Official Title:

Isokinetic Performance After Cruciate-substituting Ultra-congruent and Posterior Stabilized Total Knee Arthroplasties

NCT Number:

1585/2017

Date:

June 08, 2020

OBJECTIVE

Whether ultra-congruent (UC) or posterior cruciate ligament-stabilized (PS) inserts should be used in posterior cruciate ligament (PCL)-sacrificing total knee arthroplasty (TKA) remains debatable. Therefore, the aim of this prospective randomized controlled study is to compare the isokinetic performance and clinical outcomes of these inserts in PCL sacrificing TKA.

DESIGN AND METHODS

Sixty-six patients diagnosed with primary knee osteoarthritis will be randomly assigned to either the UC or the PS group. The Knee Society score (KSS) and isokinetic performance results for each patient will be recorded preoperatively and at 3, 6 and 12 months postoperatively. The physiatrist performing the isokinetic tests and the patients will be blinded to the study groups.

This study is approved by the institutional review board (IRB) by the “Ankara Numune Training and Research Hospital Clinical Research Ethics Committee” ethical committee (1585/2017) (Ankara, Turkey) and will be performed in accordance to the 1964 Helsinki Declaration and its amendments.

STATISTICAL ANALYSIS PLAN (SAP)

Sample size estimation is performed using the mean knee extensor peak torque at one year postoperatively, 53.9 Nm, and the standard deviation, 12, reported in a prior study [1] and G*Power (version 3.1.9.6.) software. A total of 66 patients is estimated to be needed to achieve a power of 95% in detecting a 10 Nm difference in the extensor peak torque, with a standard deviation of 12, 4 measurements, an effect size of 0.41 and a significance level (alpha) of 0.05 using two-way repeated measures ANOVA. All the data will be presented as means and standard deviations. Two-way repeated measures ANOVA will be used for the statistical analysis of the repeated measurements in the two groups. The statistical calculations will be performed with SPSS 22.0 software (IBM SPSS Statistics for Windows, version 22.0. Armonk, NY: IBM Corp.). Values of $p < 0.05$ will be considered statistically significant.

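### In its classical form the planned repeated-measures ANOVA drops a patient for an outcome after one missed test and does not adjust for baseline; a mixed model in the same software fixes both

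*Combined protocol and SAP*

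**What the plan says.** Under Design and Methods, the Knee Society score and the isokinetic results "will be recorded preoperatively and at 3, 6 and 12 months postoperatively", which makes four values per patient and outcome. The same section states: "Sixty-six patients diagnosed with primary knee osteoarthritis will be randomly assigned to either the UC or the PS group". It adds: "The physiatrist performing the isokinetic tests and the patients will be blinded to the study groups".

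The SAP section gives one method of inference: "Two-way repeated measures ANOVA will be used for the statistical analysis of the repeated measurements in the two groups". On software it says: "The statistical calculations will be performed with SPSS 22.0 software". On size it says: "A total of 66 patients is estimated to be needed to achieve a power of 95% in detecting a 10 Nm difference" in extensor peak torque, with SD 12, four measurements, effect size 0.41 and alpha 0.05. The inputs are one-year values: "Sample size estimation is performed using the mean knee extensor peak torque at one year postoperatively".

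Neither section mentions missed tests, dropout, an analysis population or adjustment for the preoperative value. The number calculated as needed and the number randomised are both 66.

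**The concern.** Classical repeated-measures ANOVA needs a full row of four values. A patient who misses one test is removed for that outcome, along with up to three values already recorded. The comparison then covers completers and no longer all randomised patients. Other outcomes, and the descriptive means and SDs, are not bound by this.

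The same analysis treats the preoperative value as a fourth outcome, so the group comparison is not adjusted for it.

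Three things are at stake:

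- recorded data that go unused;
- bias, if tests are missed for reasons tied to knee function;
- precision given up by not using baseline as a covariate.

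Blinding of the patients and the testing physiatrist makes loss driven by knowledge of the insert less likely. It does not exclude loss driven by how the knee performs.

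**Working it through.** **Inputs.** From the SAP: N = 66, difference 10 Nm, SD 12, f = 0.41 (10/12/2 = 0.417), m = 4 visits, alpha 0.05, mean 53.9 Nm. Assumed, because the documents are silent: 33 per arm, correlation rho between visits (compound symmetry) of 0.5 to 0.75 or 0.8, and the rates and patterns of missed tests.

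**1. The plan's own figure.** For the between-group effect, lambda = N × f² × m / (1 + (m − 1) × rho), referred to a noncentral F with 1 and N − 2 degrees of freedom. With rho = 0.75, lambda = 66 × 0.1681 × 4 / 3.25 = 13.65 and power is 95.3%, and 66 is the smallest even N that reaches 95%. So 66 is reproduced if rho is about 0.75, a value the SAP does not state.

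**2. Data left out.** Take 5% independent misses at each of the three post-operative visits and no missing baseline.

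- Complete patients: 66 × 0.95³ = 56.6, about 57.
- Post-operative values recorded: 198 × 0.95 = 188.1.
- Values used by the classical analysis: 198 × 0.95³ = 169.8.
- Recorded but unused: 188.1 − 169.8 = 18.3.

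**3. Power, on the plan's own terms.** Same formula, f = 0.41:

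| rho | power at 66 | power at 57 | smallest N for 95% |
|---|---|---|---|
| 0.5 | 98.6% | 97.0% | 51 |
| 0.6 | 97.5% | 95.3% | 57 |
| 0.75 | 95.3% | 92.1% | 65 |
| 0.8 | 94.5% | – | 68 |

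These figures assume that the arms differ by about 10 Nm on average over all four visits, including the one before surgery. If they differ by 0 before surgery and 10 Nm at each later visit, the four-visit average is 30/4 = 7.5 Nm and f = 7.5/24 = 0.3125. At N = 66 with complete data, lambda is 66 × 0.0977 × 4 / 2.5 = 10.3 (rho 0.5) or, with 3.25 as the divisor, 7.9 (rho 0.75). Power for the group main effect is then about 89% and 79%.

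**4. Bias among completers.** Simulated trials, 33 per arm, SD 12. Lost patients have no month-6 or month-12 value. Ranges cover rho 0.5 to 0.75.

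| Loss pattern | True difference | Lost | Bias of raw 12-month difference |
|---|---|---|---|
| (a) lowest month-3 scorers in one arm, equal random loss in the other | 0 | 3 per arm | +1.0 to +1.6 Nm |
| (a) as above | 0 | 5 per arm | +1.6 to +2.4 Nm |
| (b) lowest month-3 scorers in each arm | 0 | 3 or 5 per arm | about 0 |
| (c) lowest month-3 scorers of all 66 | 10 Nm after surgery, 0 before | 6 in all | −1.2 to −1.8 Nm |
| (c) as above | as above | 10 in all | −1.5 to −2.5 Nm |

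The group main effect over four visits is biased in (a) and (c) by about 1.3 to 2.7 Nm in absolute size. The baseline-to-12-month change contrast is within about 0.05 Nm of the truth in (a) and (c), because under compound symmetry selection on month 3 shifts baseline and month 12 equally. The mixed model's 12-month difference was within 0.06 Nm of the truth in all the settings.

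**5. Precision of the 12-month difference, 5% independent misses.**

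| Analysis | SD, rho 0.5 | SD, rho 0.75 |
|---|---|---|
| Completers, unadjusted | 3.20 Nm | 3.18 Nm |
| Completers, baseline-adjusted | 2.79 Nm | 2.14 Nm |
| Mixed model, baseline-adjusted | 2.60 Nm | 2.02 Nm |

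Share of the gain due to the covariate: (3.20 − 2.79)/(3.20 − 2.60) = 0.41/0.60, about two-thirds; (3.18 − 2.14)/(3.18 − 2.02) = 1.04/1.16, about nine-tenths.

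**The case against.** The strongest reply is that the plan never says incomplete patients will be dropped. SPSS has a mixed-model procedure, the SAP does not say which procedure it means, and if no test is missed nothing is lost. That stands. Deletion is a consequence of the classical form and not a stated rule, and no attrition rate is given. But a plan that leaves this open lets the choice be made after the data are seen.

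A second reply concerns bias. A reader might infer that the trial's result will be biased, or that a true 10 Nm would be reported as about 7.5 to 8.9 Nm. The documents do not support so broad a claim. Those figures belong to the raw 12-month difference in one severe pattern. The ANOVA also tests group by visit, and the change contrast within that effect is about unbiased in the same simulations. That zero rests on compound symmetry, and the group main effect is not protected. With the same loss rule in both arms and no true difference there is no bias to speak of.

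A third reply concerns precision. A reader might credit the mixed model's smaller SD to the values it rescues. Most of it is baseline adjustment, which completers could have too.

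Finally, a mixed model with baseline as covariate would itself drop a patient whose baseline is missing, unless a rule is written.

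**Conclusion.** The point holds as a cheap improvement that should be made. The only named analysis, in its classical form, discards recorded values after any missed test, confines the comparison to completers, and leaves the preoperative value unused as a covariate.

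The size cannot be fixed from the documents. It rests on assumed rates of missed tests, an assumed correlation of 0.5 to 0.75, and loss patterns chosen to be severe.

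It would go too far to say that missed tests leave the trial underpowered: at 57 complete patients, power on the plan's terms runs from 97.0% to 92.1% for rho 0.5 to 0.75. It would equally go too far to take comfort from those figures, since they assume a difference that is already present before surgery. With a difference only after surgery, main-effect power is about 89% to 79% even with no missed test. The SAP does not say which ANOVA effect decides the trial, so that is not the power of the analysis as a whole. Confidence is medium.

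**What to change.** Replace the ANOVA with a linear mixed model (SPSS MIXED):

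- outcomes: the 3-, 6- and 12-month values;
- covariate: the preoperative value;
- fixed effects: group, visit and group by visit;
- unstructured covariance over visits;
- population: every randomised patient with at least one post-operative value, in the assigned group.

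If a baseline is missing, fill it with the mean over both arms, or put baseline in the outcome vector with a mean common to both arms, so that the patient is kept.

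Report the adjusted group difference with its 95% confidence interval at each visit, with 12 months as the main contrast, which matches the time point of the sample-size inputs. Report missing values by arm and visit, with reasons. State that the model assumes missing at random and that the 95% power figure makes no allowance for missed tests. A sensitivity analysis for values missing not at random is optional.

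The cost is revised SAP wording, different syntax in the same software, slightly more analysis work, and reliance on missing at random. No extra patients or visits are needed.

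### The SAP does not say which ANOVA effect decides UC versus PS, and the effect that its 66 patients fit is diluted by the preoperative visit

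*Combined protocol and SAP*

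**What the plan says.** The Objective section sets out to "compare the isokinetic performance and clinical outcomes of these inserts in PCL sacrificing TKA". Under Design and Methods, the Knee Society score (KSS) and the isokinetic results are "recorded preoperatively and at 3, 6 and 12 months postoperatively", so one of the four measurements comes before the intervention.

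The SAP section opens with the sizing: "Sample size estimation is performed using the mean knee extensor peak torque at one year postoperatively, 53.9 Nm, and the standard deviation, 12". It arrives at 66 patients and 95% power for "detecting a 10 Nm difference in the extensor peak torque, with a standard deviation of 12, 4 measurements, an effect size of 0.41", at alpha 0.05. The borrowed mean and SD are one-year values, but the 10 Nm is not tied to any visit. The correlation between visits is not given.

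The analysis itself is one sentence: "Two-way repeated measures ANOVA will be used for the statistical analysis of the repeated measurements in the two groups". The decision rule is that p-values below 0.05 "will be considered statistically significant". The SAP gives no primary outcome, no deciding effect within the ANOVA and no rule for multiple tests.

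**The concern.** Naming a two-way repeated measures ANOVA does not name a test. It produces a group effect, a time effect and a group-by-time effect. Two of these bear on UC versus PS, and they answer different questions. The group effect asks whether the arms differ on the average of all four visits. The group-by-time effect asks whether the difference changes across visits.

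Two things are at stake. First, if the choice is left open, the effect that supports a claim can be picked after the data are seen. Second, the effect that matches the sample size is a poor one for this design. Randomisation makes the expected preoperative difference zero, so including that visit in the average shrinks any postoperative difference by a quarter.

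**Working it through.** **Inputs.** From the SAP: difference 10 Nm, SD 12, m = 4 measurements, f = 0.41, alpha 0.05, N = 66, power 95%. From Design and Methods: one preoperative and three postoperative visits. Assumed, because the document does not give them: 1:1 allocation (33 per arm), equal variances and equal correlation ρ between visits (compound symmetry), no dropout. ρ itself is varied.

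**Step 1: reproduce N = 66.** Two means 10 apart with SD 12 give f = (10/2)/12 = 0.417, which the SAP states as 0.41.

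- Group effect: λ = N f² m / (1 + (m − 1)ρ), with 1 and N − 2 df. At f = 0.41 and ρ = 0.75, λ = 66 × 0.1681 × 4 / 3.25 = 13.65, and power is 95.35%. The smallest even N for 95% is 52 at ρ = 0.5, 62 at 0.7, 66 at 0.75 and 68 at 0.8. N = 66 results for ρ = 0.737 to 0.770 (f = 0.41) or 0.772 to 0.807 (f = 5/12).
- Group-by-time: λ = N f² m / (1 − ρ), with 3 and 3(N − 2) df. This needs 28 at ρ = 0, 16 at 0.5 and 8 at 0.75 (f = 0.41), never 66.
- Single-visit two-sided t test, 33 per arm: power 90.7% (d = 0.82) to 91.5% (d = 0.833), not 95%.

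The stated figure is therefore reproduced by the group effect at ρ of about 0.74 to 0.81.

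**Step 2: put the difference only after surgery.** The four-visit mean difference is (0 + 10 + 10 + 10)/4 = 7.5 Nm. The variance of a patient's four-visit mean is 144(1 + 3ρ)/4. At ρ = 0.75 that is 117, so λ = (33/2) × 7.5²/117 = 7.93. Had all four visits differed by 10 Nm, λ would be (33/2) × 100/117 = 14.10, with power 95.9%.

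**Step 3: the other effect, same pattern.** The half-differences are 0, 5, 5, 5 with mean 3.75, and their squared deviations sum to 3.75² + 3 × 1.25² = 18.75. Then λ = 66 × 18.75 / (144(1 − ρ)) = 8.594/(1 − ρ).

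| ρ (assumed) | Group effect, 0/10/10/10 Nm | Group-by-time, 0/10/10/10 Nm | Consistent with N = 66? |
|---|---|---|---|
| 0.3 | 95.2% | 84.1% | no |
| 0.5 | 88.5% | 94.6% | no |
| 0.75 | 79.2% | 99.9% | yes |
| 0.80 | 77.4% | over 99.9% | yes |

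Simulation of the group effect (40,000 trials per value) gave 79.5% at 0.75 and 77.1% at 0.80. Pairing each f with the ρ values at which it yields exactly 66 gives 77.2% to 78.4%.

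If the 10 Nm appeared only at 12 months, the average would be 2.5 Nm. At ρ = 0.75 the group effect would have about 15% power and the group-by-time test 99.9%.

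**Step 4: false positives on torque.** If either effect may support a claim, and the two are independent under sphericity, the rate is 1 − 0.95² = 9.75%. Simulation gave 9.5% to 10.0%.

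**Step 5: a baseline-adjusted test instead.**

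- 12-month ANCOVA: variance 144(1 − r²), where r is the correlation with preoperative torque, 63 df. At r = 0.5, λ = (33/2) × 100/108 = 15.28. Power is 91.5% with no baseline correlation, 93.7% at r = 0.3, 97.1% at 0.5 and over 99% at 0.75 to 0.80. It first reaches 95% at r of about 0.39.
- Mean of the three postoperative visits, adjusted for baseline: variance 144[(1 + 2ρ)/3 − ρ²], which is 63.8 at ρ = 0.3, 60 at 0.5, 39 at 0.75 and 32.6 at 0.80. With 10 Nm at all three visits, power is over 99% throughout.

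**The case against.** The strongest reply is that the plan specifies the whole ANOVA. Its group-by-time test has more than 99.9% power for a postoperative-only difference at the correlations implied by N = 66, so such a difference would hardly be missed. That is correct. A reader might infer that the trial is too small, or that a real 10 Nm would be missed 21% to 23% of the time. The document does not support either as a general statement: the second holds only if the group effect alone decides, and the SAP does not say so. Equally, a 9.8% error rate applies only if either effect may count. The two harms belong to two different readings of the same sentence and cannot be added together.

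It is also fair to say that the correlation is inferred. At 0.3 the group effect keeps 95.2%, slightly more than the 12-month ANCOVA (93.7%). But the SAP's own calculation would then have returned about 40 patients, not 66.

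Finally, torque is the only outcome with a sizing calculation and is evidently the lead outcome. Larger false-positive rates can be produced by adding KSS, further isokinetic variables or a separate 12-month test. They would rest on tests or correlations that the plan does not contain, and are not claimed here.

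What stands is that the deciding effect is unnamed, and that the one matching the sample size includes a visit at which no treatment effect can exist.

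**Conclusion.** The point holds as a fault in the choice and naming of the deciding test. Read as the group effect, which is what N = 66 fits, the plan has about 77% to 79% power for a 10 Nm difference confined to the three postoperative visits, against the stated 95%. This rests on a correlation of about 0.74 to 0.81 back-calculated from N = 66, and on 1:1 allocation, compound symmetry and no dropout. Read as group-by-time, the same data give over 99%. If either may count, the error rate on torque is about 9.8%; with one test named in advance it stays at 5%.

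A reader might also take the trial to be sized on a 12-month difference. Only the mean and SD are one-year values; the 10 Nm has no visit attached, and the calculation uses four measurements. A 12-month deciding test is therefore one reasonable choice, not something already in the plan.

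**What to change.** Add a short paragraph to the SAP, before the data are examined, that:

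1. names knee extensor peak torque as the primary outcome;
2. names one deciding test that uses preoperative torque as a covariate and not as an outcome visit: the UC–PS difference at 12 months, or the mean of the three postoperative visits if the sponsor prefers to keep the repeated measures;
3. sets two-sided alpha at 0.05 and reports the difference with its 95% CI;
4. restates the power for that test, with the assumed correlation written down;
5. makes the ANOVA group and group-by-time effects, KSS and the other isokinetic variables secondary.

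The choice in item 2 has a trade-off. The postoperative mean is the more powerful if the difference is present from 3 months, but it would itself be diluted if the difference appeared only late.

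The cost is SAP wording; no visits or data are added. Secondary p-values lose confirmatory status. With the 12-month test and 66 patients, the stated 95% must be lowered if the baseline correlation is below about 0.39, to 91.5% at worst. Holding 95% there would take 36 per arm (72) at a correlation of 0.3, or 39 per arm (78) with none. At the 0.75 to 0.80 that N = 66 implies, no extra patients are needed.
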